## Appendix 1 Schedule of Activities for Patients with Follicular Lymphoma (Dose-Escalation and Expansion) (cont.)

	Screening a		Induction (6 Cycles; 28-Day Cycles)								EOI	Maint. (24 Months)	EOM b	Post-Treatment FU Period (Q3M) d	Survival FU Period (Q3M) d
	D • 28 to D • 1	D • 14 to D • 1	Cycle 1 (± 1 d)				Cycle 2 (± 2 d)		Cycles 3•6 (± 2 d)		After Last Induction Dose c	Every 2 Months (± 1 wk)	35 Days After Last Dose		
			D1	D5	D8	D15	D1	D15	D1	D15		D1			
Serum chemistry q		x	x o, p		x p	x p	x p	x	x p	x	x g	x	x		
Coagulation (INR, aPTT [or PTT], and PT)		x													
Pregnancy test r		x									x g		x		
Hepatitis B and C testing s	x														
Quantitative IgA, IgG, IgM			x								x	x t	x	x u	
PK sample for obinutuzumab			x v												
PK sample for idasanutlin			x v												
Whole blood for MRD w			x p				x				x	x t	x		
Whole blood for lymphocyte immunophenotyping x			x p			x p	x p			x p	x	x t	x	x u	
Serum for MIC-1			x v	x v			x v,y			x v,z					
Optional peripheral blood sample for RCR aa			x	x											
Tumor tissue specimen (leftover tissue may be used for optional RCR specimen bb )	x bb		x cc												

## Appendix 1 Schedule of Activities for Patients with Follicular Lymphoma (Dose-Escalation and Expansion) (cont.)

	Screening a		Induction (6 Cycles; 28-Day Cycles)								EOI	Maint. (24 Months)	EOM b	Post-Treatment FU Period (Q3M) d	Survival FU Period (Q3M) d	
	D • 28 to D • 1	D • 14 to D • 1	Cycle 1 (± 1 d)				Cycle 2 (± 2 d)		Cycles 3•6 (± 2 d)		After Last Induction Dose c	Every 2 Months (± 1 wk)	35 Days After Last Dose			
			D1	D5	D8	D15	D1	D15	D1	D15		D1				
Concomitant medications	x		To be recorded continually until end of treatment													
Adverse events dd	x		To be assessed continually dd													
PET-CT scan	x ee											x ff	x gg			
CT scan hh	x hh							x oo				x ff	x ii	x jj	x kk	
Bone marrow biopsy and aspirate	x ll											x ff,mm	x mm	x jj,mm		
Study treatment administration	Obinutuzumab nn		x		x	x	x			x			x			
	Idasanutlin nn			D1-D5					D1-D5		D1-D5			x pp		
New anti-lymphoma treatment															x	x
Survival follow-up																x

CT = computed tomography; D = day; Discont. = discontinuation; ECOG = Eastern Cooperative Oncology Group; eCRF = electronic Case Report Form; EOI = end of induction; EOM = end of maintenance; FLIPI = Follicular Lymphoma International Prognostic Index; FU = follow-up; Maint. = maintenance; MRD = minimal residual disease; MIC = macrophage inhibitory cytokine-1; MRI = magnetic resonance imaging; PET = positron emission tomography; PK = pharmacokinetic; Q3M = every 3 months; RCR = Roche Clinical Repository; wk = week.

Notes: On treatment days, all assessments should be performed prior to dosing, unless otherwise specified.

Assessments shaded in gray should be performed as scheduled, but the associated data do not need to be recorded on the eCRF (except in the case of an adverse event).

## Appendix 1 Schedule of Activities for Patients with Follicular Lymphoma (Dose-Escalation and Expansion) (cont.)

- 
- a The screening period starts with the signing of the Informed Consent Form. Results of standard-of-care tests or examinations performed prior to obtaining informed consent and within the defined window may be used as screening and baseline assessments; such tests do not need to be repeated for screening purposes.
- b Patients who complete maintenance treatment or discontinue maintenance treatment prematurely will undergo assessments at EOM.
- c EOI assessments should be performed 6•8 weeks after Day 1 of the last induction cycle. As an exception, patients who discontinue induction treatment prematurely because of an adverse event may undergo EOI assessments 4•8 weeks after their last dose of study treatment.
- d Patients who complete treatment or discontinue treatment for reasons other than disease progression will undergo assessments every 3 months during the post-treatment FU period, which will continue until disease progression, the start of new anti-lymphoma treatment, or the end of the study, whichever occurs first. The first post-treatment FU visit is 3 months after the EOI visit for patients who do not receive maintenance treatment and 3 months after the last dose for patients who receive maintenance treatment. Patients who experience disease progression will undergo limited assessments every 3 months during the survival FU period, which will continue until the end of the study. The end of the study is defined as the time when all enrolled FL patients have completed or discontinued study treatment and all enrolled DLBCL patients have been followed for at least 1 year after they have completed or discontinued study treatment.
- e Informed consent must be documented before any study-specific screening procedure is performed.
- f Vital signs include respiratory rate, pulse rate, body temperature, and systolic and diastolic blood pressures while the patient is in a seated position. For obinutuzumab infusions: For the first cycle and for patients who experience an infusion-related reaction, vital signs will be measured prior to the infusion, every 15 ( $\pm$  5) minutes for the first 90 minutes of the infusion, and then every 30 ( $\pm$  10) minutes until 1 hour after completion of the infusion. For the second and subsequent cycles, vital signs will be measured every 30 minutes during the infusion, except in patients who had experienced an infusion-related reaction during a prior infusion.
- g Perform only in patients who will not be receiving maintenance treatment.
- h All ECGs should be collected prior to and 6 hours after idasanutlin administration or after obinutuzumab administration, whichever occurs later. For Cycle 1 Day 5 in the induction phase, perform ECG 6 hours post idasanutlin administration only if patient is still at clinic.
- i All ECGs should be collected prior to and 6 hours after idasanutlin administration or after obinutuzumab administration, whichever occurs later. ECGs will be performed as described on Cycle 4, Days 1 and 5 only. For Cycle 4 Day 5, perform ECG 6 hours post idasanutlin administration only if patient is still at clinic.
- j Includes evaluation of the head, eyes, ears, nose, and throat and the cardiovascular, dermatological, musculoskeletal, respiratory, gastrointestinal, genitourinary, and neurological systems. Record abnormalities observed at baseline on the General Medical History and Baseline Conditions eCRF.
- k As part of tumor assessment, the physical examination should include evaluation for the presence of enlarged nodes, palpable hepatomegaly, and splenomegaly. This information will be recorded on the appropriate tumor assessment eCRF.
- l Includes systems of primary relevance (e.g., cardiovascular and respiratory systems), systems associated with symptoms (newly emergent or monitored from baseline), and areas associated with tumor assessment (lymph nodes, liver, spleen, and any other areas identified at baseline). Record new or worsened clinically significant abnormalities on the Adverse Event eCRF.

## Appendix 1

### Schedule of Activities for Patients with Follicular Lymphoma (Dose-Escalation and Expansion) (cont.)

- m Unexplained fever > 38°C, nightsweats, unexplained weight loss > 10% of body weight over 6 months.
- n Includes hemoglobin, hematocrit, platelet count, RBC count, WBC count, and percent or absolute WBC differential count (neutrophils, eosinophils, basophils, monocytes, lymphocytes, other cells).
- o Screening laboratory assessments may be used for Day 1 of Cycle 1 if performed within 72 hours prior to Day 1 of Cycle 1.
- p Perform hematology and chemistry tests within 72 hours prior to Day 1 of each cycle and within 24 hours prior to Days 8 and 15 of Cycle 1. Samples for exploratory biomarker research should be collected at the same time as hematology and chemistry samples.
- q Includes sodium, potassium, glucose, BUN or urea, creatinine, calculated creatinine clearance, calcium, total bilirubin, direct bilirubin, total protein, albumin, ALT, AST, alkaline phosphatase, amylase, lipase, LDH, and uric acid.
- r All women who are not postmenopausal (• 12 months of non-therapy-induced amenorrhea) or surgically sterile will have a serum pregnancy test at screening within 7 days prior to Day 1 of Cycle 1. Because of the suspected effect of idasanutlin on embryo-fetal development, monthly pregnancy testing is strongly recommended for women of childbearing potential ([CTFG 2014](#)).
- s Includes hepatitis B surface antigen, total hepatitis B core antibody, and hepatitis C virus antibody.
- t Perform at the same time as tumor assessments at 12, 18, and 24 months after initiation of induction treatment.
- u Perform every 3 months until recovery to either normal range or baseline level, disease progression, or the start of new anti-lymphoma treatment, whichever occurs first.
- v See [Appendix 3](#) and [Appendix 4](#) for detailed schedule.
- w Includes circulating lymphoma cells and/or cell-free circulating tumor DNA.
- x Includes B-cell counts (CD19), T-cell counts (CD3, CD4, and CD8), and NK-cell counts (CD16 and CD56).
- y Also on Day 5 of this cycle. See [Appendix 3](#) and [Appendix 4](#) for detailed schedule.
- z Cycle 4 Day 1 and Day 5. See [Appendix 3](#) and [Appendix 4](#) for detailed schedule.
- aa Requires separate patient consent for RCR participation. Not applicable for a site that has not been granted approval for RCR sampling.
- bb Availability of adequate archival or freshly biopsied tumor tissue samples should be confirmed at screening (see [Section 4.5.6.2](#) for details).
- cc A tumor biopsy sample is preferred and recommended at the time of progression unless no adequate tumor site is accessible.
- dd After informed consent has been obtained but prior to initiation of study treatment, only serious adverse events caused by a protocol-mandated intervention should be reported. After initiation of study treatment, all adverse events will be reported until 90 days after the last dose of study treatment. After this period, the Sponsor should be notified if the investigator becomes aware of any serious adverse event that is believed to be related to prior study treatment (see [Section 5.6](#)). An exception is made for Grade 3–4 infections (related and unrelated), which should be reported until up to 2 years after the last dose of study treatment. The investigator should follow each adverse event until the event has resolved to baseline grade or better, the event is assessed as stable by the investigator, the patient

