### **3.1.2            Dose-Escalation Phase (Part 1)**

The purpose of the dose-escalation phase (Part 1) is to identify the RP2D *and regimen* for idasanutlin when combined with a fixed dose of 1000 mg of obinutuzumab in patients with R/R FL and *the RP2D for idasanutlin when combined with 375 mg/m^2 of rituximab in patients with R/R DLBCL*. The RP2D will be based on MTD of idasanutlin when combined with a fixed dose of obinutuzumab *or with 375 mg/m^2 of rituximab*, but will also include all safety data during treatment. *There could be two different RP2Ds and/or regimens dependent on the combinations of idasanutlin plus obinutuzumab or idasanutlin plus rituximab.*

During the escalation phase, approximately 9• 40 patients will be enrolled in dosing groups of 3• 6 patients each and will be treated at escalating doses of idasanutlin in accordance with the treatment regimen and dose-escalation rules described in Section 3.1.2.2.

Patients will be closely monitored for adverse events during a DLT assessment window, defined as the first treatment cycle *for Regimen A and the first two treatment cycles (one cycle of idasanutlin combination treatment) for patients enrolled in bridging cohort(s) in which idasanutlin will start at Cycle 2 (Regimen B)*. See Section 3.1.2.2 for treatment regimens. Adverse events meeting the criteria for DLT, as defined below (see Section 3.1.2.1), will be reported to the Sponsor within 24 hours (see Section 5.4.2).

Patients experiencing a DLT during the *DLT window* will permanently discontinue study treatment.

Patients who discontinue from the study prior to completing the DLT assessment window for reasons other than a DLT will be considered non-evaluable for dose-escalation decisions and MTD assessments and will be replaced by an additional patient at that same dose level who has not been previously treated in the study. Patients who miss one or more doses of obinutuzumab, *rituximab*, or idasanutlin during the DLT assessment window for reasons other than a DLT will also be replaced.

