### 3.1.2.1 Definition of Dose-Limiting Toxicity

In this study, a DLT is defined as at least one of the following events occurring during the first cycle (*or the first two cycles in the bridging cohorts for patients with FL who start idasanutlin at Cycle 2*) of treatment and assessed by the investigator as not clearly related to the patient's underlying disease:

- *Any Grade 5 adverse event unless unequivocally due to the underlying malignancy or extraneous causes*
- Adverse event of any grade that leads to a delay of more than 14 days in the start of the next treatment cycle
- Grade 3 or 4 non-hematologic adverse event, with the following exceptions:
  - Grade 3 or 4 IRRs
    - Note that IRRs are not dose-dependent events. They may occur even after a small amount of drug has been administered.
    - Grade 3 diarrhea that responds to adequate therapy within 48 hours
    - Grade 3 nausea or vomiting that occurs in the absence of premedication and responds to adequate therapy within 72 hours
- *Any increase in hepatic transaminase > 3 • baseline and an increase in direct bilirubin > 2 • ULN, without any findings of cholestasis or jaundice or signs of hepatic dysfunction and in the absence of other contributory factors (e.g., worsening of metastatic disease or concomitant exposure to known hepatotoxic agent or of a documented infectious etiology) is suggestive of potential drug induced liver injury (according to Hy's Law) and will be considered a DLT*
- Hematologic adverse events that meet any of the following criteria:
  - Grade 3 or 4 neutropenia in the presence of sustained fever of >38°C (lasting >5 days) or a documented infection
  - Grade 4 neutropenia lasting >7 days
  - Grade 3 or 4 thrombocytopenia *if associated with Grade ≥ 3 bleeding*
  - Grade 4 thrombocytopenia lasting >7 days

Other toxicities that are considered clinically relevant and related to study treatment as determined by the investigator and the Medical Monitor may also be considered DLTs.

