**Table 2 Induction Treatment for Dose-Escalation Phase**

Dose-Escalation, FL and DLBCL Patients (28-Day Cycles): Regimen A	
Cycle 1	DLT period 
 
• Obinutuzumab 1000 mg IV on Days 1, 8, and 15
 
• Idasanutlin, oral Days 1•5, starting dose 100 mg QD, minimal clinically and pharmacologically feasible dose-escalation steps 50 mg
 

Cycles 2•6	
 
• Obinutuzumab 1000 mg IV on Day 1
 
• Idasanutlin, oral Days 1•5, starting dose 100 mg QD
 

Dose-Escalation Bridging Cohort, DLBCL Patients Only (28-Day Cycles)	
Cycle 1	DLT period 
 
• Rituximab 375 mg/m^2 IV on Day 1
 
• Idasanutlin, oral Days 1•5, starting dose MTD identified in combination with obinutuzumab with Regimen A, minimal clinically and pharmacologically feasible dose-escalation steps 50 mg
 

Cycles 2–6	
 
• Rituximab 375 mg/m^2 IV on Day 1
 
• Idasanutlin, oral Days 1•5, starting dose MTD identified in combination with obinutuzumab
 

Dose-Escalation Bridging Cohort, FL Patients Only (28-Day Cycles): Regimen B	
Cycle 1	
 
• Obinutuzumab 1000 mg IV on Days 1, 8, and 15
 

Cycles 2–6	
 
• Obinutuzumab 1000 mg IV on Day 1
 
• Idasanutlin, oral Days 1•5, starting dose MTD identified in combination with obinutuzumab with Regimen A during dose escalation, minimal clinically and pharmacologically feasible dose-escalation steps 50 mg
 

DLT period will be Cycles 1 and 2.	

*DLBCL =diffuse large B-cell lymphoma; DLT = dose-limiting toxicity; FL =follicular lymphoma; IV=intravenous; MTD =maximum tolerated dose; QD=once a day.*

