### 3.3.3 Rationale for Dosing Regimen

There is a standard regimen for obinutuzumab used in all pivotal NHL studies of a fixed dose of 1,000 mg (see the Obinutuzumab Investigator’s Brochure) in combination with several cytotoxic drugs. These data support this efficacious fixed dose as the basis for combinations of obinutuzumab with targeted drugs. Obinutuzumab at a fixed dose of 1,000 mg is also being studied in combination with other targeted agents in a number of ongoing clinical studies, including MPDL3280A (GO29383), polatuzumab vedotin (GO27834), and venetoclax (GP28331, GO27878).

*The study will start with obinutuzumab standard dosing in combination with idasanutlin from Cycles 1 to 6 (Regimen A). For patients with FL, an alternative dosing regimen (Regimen B) with obinutuzumab given at Cycle 1 followed by obinutuzumab in combination with idasanutlin from Cycles 2 to 6 will be explored (bridging cohorts) to investigate the possibility of alleviating hematological toxicities at Cycle 1. The rationale for exploring Regimen B in patients with FL is that obinutuzumab is given 3 times during Cycle 1 (Days 1, 8, and 15) compared to only on Day 1 in subsequent cycles. Those 3 doses of obinutuzumab, when combined with idasanutlin at higher doses in the same treatment cycle, may induce more profound hematologic toxicities. Staggered idasanutlin dosing to start at Cycle 2 may mitigate toxicities and allow recovery before dosing with the combination. Only one regimen will be chosen for the expansion phase.*

*The dose of rituximab of 375mg/m^2 is the recommended dose in the NHL population and is the standard of care. For DLBCL patients in the bridging cohort(s) and the expansion phase, the dose and schedule of rituximab in the induction regimen will be 375 mg/m^2 on Day 1 of each 28-day cycle (Cycles 1•6). The dose and schedule in the consolidation phase will be 375 mg/m^2 every 2 months in combination with idasanutlin to explore potential benefit with consolidation treatment. For patients receiving rituximab, no alternative regimen will be explored as rituximab is only given at Day 1 in each treatment cycle and the overlapping toxicities with idasanutlin are expected to be less pronounced.*

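### Appendix 1 was not adapted to Regimen B: its first idasanutlin cycle has no scheduled ECG and one fewer post-dose blood count than Regimen A's

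*Combined protocol and SAP*

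**What the plan says.** Appendix 1 covers all follicular lymphoma (FL) patients in escalation and expansion and has no Regimen B columns. Haematology is marked on Days 1, 8 and 15 of Cycle 1, and then on Days 1 and 15 of each later induction cycle. Footnote p ties the additional counts to the first cycle: "within 24 hours prior to Days 8 and 15 of Cycle 1".

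Dosing-timed ECGs are marked on Cycle 1 Days 1 and 5. Footnote h says: "For Cycle 1 Day 5 in the induction phase, perform ECG 6 hours post idasanutlin administration only if patient is still at clinic". For the rest of induction, footnote i says: "ECGs will be performed as described on Cycle 4, Days 1 and 5 only".

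Table 2 gives Regimen B obinutuzumab alone in Cycle 1, with idasanutlin on Days 1-5 from Cycle 2, and adds: "DLT period will be Cycles 1 and 2". Section 3.3.3 says Regimen B is explored "to investigate the possibility of alleviating hematological toxicities at Cycle 1" and that one regimen goes forward to the expansion phase. Among the haematologic DLT criteria in Section 3.1.2.1 are "Grade 4 neutropenia lasting >7 days" and "Grade 4 thrombocytopenia lasting >7 days".

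Appendix 4, written for Regimen B, puts the dense Day 5 idasanutlin PK and MIC-1 sampling in Cycle 2.

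**The concern.** The DLT window and the PK schedule were changed to follow idasanutlin into Cycle 2. The safety counts and ECGs were not, and no reason is given.

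This matters most for haematologic toxicity, because Regimen B exists to see whether staggering reduces it. Section 1.4 names thrombocytopenia and neutropenia as the main DLTs of earlier work and records one prolonged thrombocytopenia among three NHL patients. Table 14 gives Grade 3 or higher rates of 44% and 27% with 5-day dosing. In Regimen B's first idasanutlin cycle, 14 days pass between the Day 1 and Day 15 counts, so an episode that meets a criterion of more than 7 days could start and end between them.

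ECG change is a separate matter. It is a named safety endpoint (Section 2.1), and Section 6.3 plans QT and QTcF summaries, yet Regimen B has no recording around its first idasanutlin doses. If Regimen B is chosen, the same schedule governs about 40 FL patients in the expansion phase.

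**Working it through.** **Scheduled looks, from Appendix 1 and Table 2**

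| | Regimen A | Regimen B |
|---|---|---|
| Post-dose counts, first idasanutlin cycle | 3 (C1 D8, C1 D15, C2 D1) | 2 (C2 D15, C3 D1) |
| Post-dose counts, whole DLT window | 3 | 5 (C1 D8, C1 D15, C2 D1, C2 D15, C3 D1) |
| ECG visits, first idasanutlin cycle | 2 (D1, D5) | 0 |
| First scheduled ECG on idasanutlin | Cycle 1 | Cycle 4 |

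The first three of Regimen B's five counts are taken before any idasanutlin.

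**Measure 1: does any scheduled count fall inside the episode?** The documents give no nadir day, so onset and duration are assumptions. Let the episode run from day s to day s + L of the idasanutlin cycle. A count on day t falls inside it when t − L ≤ s ≤ t. Take L = 8 (just over the threshold) and s uniform over Days 3-18, a range of 15 days.

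- The Day 8 count covers s from 3 to 8.
- The Day 15 count covers s from 7 to 15.
- The count before the next cycle, on Days 26-28, covers s from 18 at the earliest.
- Regimen A misses s from 15 to 18: 3/15 = 20%.
- Regimen B misses s from 3 to 7 and from 15 to 18: (4 + 3)/15 = 47%.

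The difference is (12 − L)/15 for L from 8 to 12. That is 4/15 (27 points) at 8 days, 2/15 (13 points) at 10 days and zero at 12 days. At 10 days the levels are 7-20% in A and 20-33% in B, depending on the day of the last count. Restricting onset to Days 3-10 with L = 8 gives 4/7 = 57% in B and 0% in A. For onset after Day 8 the two schedules perform alike.

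**Measure 2: is the episode documented as lasting more than 7 days?** Assume it is dated from the first scheduled count that shows it and then followed daily. Take onset uniform over Days 4-8 (mean 6) and duration uniform from 7 to 2m − 7 days, with mean m. Regimen A needs L > 15 − s, with probability (2m − 16)/(2m − 14). Regimen B needs L > 22 − s, with probability (2m − 23)/(2m − 14), or zero if negative.

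| Mean duration | A | B |
|---|---|---|
| 10 days | 4/6 = 67% | 0% |
| 14 days | 12/14 = 86% | 5/14 = 36% |
| 21 days | 26/28 = 93% | 19/28 = 68% |

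With onset on Day 8 or later there is again no difference.

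**What one unseen DLT changes.** Section 3.1.2.3 says that after 0 of 3 DLTs at 100 mg, the dose following a cohort of 3 at 250 mg is 300, 250 or 200 mg for 0, 1 or 2 DLTs. Rebuilding the stated model (reference dose 300 mg, prior variances 2.661 and 1.816, loss weights 1, 0, 1, 2, stated increment limits) returns the same three values. With 3 DLTs the rebuild gives 150 mg against the stated 100 mg, a case not used here. One unseen DLT therefore moves this example up by one 50 mg step. The model for Regimen B is described only as similar and its prior is not given, so this is an illustration.

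**The case against.** A reader might infer that haematologic DLTs are looked for less often in Regimen B and that the choice of regimen is tilted toward B. The documents do not support that.

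- Over its DLT window Regimen B has more scheduled counts, 5 against 3. Its window also includes an obinutuzumab-only cycle in which DLTs count, which pushes the other way.
- No numerical rule for choosing between A and B is given, and Section 3.1.2 bases the recommended dose on all safety data.
- Only the two Grade 4 criteria of more than 7 days depend mainly on mid-cycle counts. Fever, infection and Grade 3 or higher bleeding present clinically, and the cycle-delay criterion uses the pre-cycle count that both regimens have.
- The percentages need early onset, and on the first measure a short episode. Section 5.1.3.2 warns of long-lasting thrombocytopenia, for which the first measure shows no gap. Visit windows of 1 to 2 days are ignored.

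Sections 5.1.1.4 and 5.1.3.2 also call for close monitoring. That does not close the gap: Section 5.1.3.2 refers back to the Appendix 1 schedule, and neither section adds a scheduled count.

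On ECGs, it would be wrong to say that Regimen B has no Day 5 value on idasanutlin, because Cycle 4 Day 5 is scheduled. Footnote h also times recordings to obinutuzumab, so the Cycle 1 Day 1 ECG keeps a purpose, and the Day 5 six-hour recording is conditional even in Regimen A. Section 1.3.3.1 reports no apparent correlation between idasanutlin concentration and QTcF, which lowers the stakes. ECGs have no bearing on haematologic DLTs.

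**Conclusion.** The mismatch stands on the text. In Regimen B's first idasanutlin cycle the plan schedules 2 post-dose counts against 3 in Regimen A and no ECG against two ECG visits.

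The effect on DLT ascertainment is conditional. For Grade 4 cytopenia starting before about Day 8, Regimen B can miss or under-date more episodes: 47% against 20% with no count inside an 8-day episode under the uniform-onset assumption. This could favour B in the comparison, but the net direction and size cannot be established from the documents. The ECG gap is a separate weakness in a named safety endpoint. Confidence is moderate: high for the schedule mismatch, limited for its consequence because onset and duration are assumed.

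**What to change.** Reconcile Appendix 1 with the Regimen B DLT window in Section 3.1.2 and Table 2, and with Appendix 4. The aim is that safety counts and idasanutlin-timed ECGs in the first idasanutlin cycle are comparable between Regimens A and B. Separate Regimen B columns, as Appendix 4 already provides for PK, would do this. The sponsor should set the exact days and decide whether to keep the ECG around the first obinutuzumab infusion.

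The cost is an edit to Appendix 1 and at most one added local blood count, possibly with a visit, per Regimen B patient. ECGs could use Cycle 2 Days 1 and 5, when Appendix 4 already has the patient sampled up to 6 hours after idasanutlin. Keeping the first-obinutuzumab ECG as well would add recordings rather than only move them.
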